7. CRITERIA FOR STUDY DISCONTINUATION GENERAL

CRITERIA

- Inability of patient to comply with study requirements
- Determination by the investigator that it is no longer safe for the patient to continue therapy
- Disease progression
- Patient's preference

The responsible local clinical Investigator as well as MDACC IND Office, Celgene and Genentech have the right to discontinue this study at any time for reasonable medical or administrative reasons in any single center. Possible reasons for termination of the study could be but are not limited to:

- Unsatisfactory enrollment with respect to quantity or quality
- Inaccurate or incomplete data collection
- Falsification of records
- Failure to adhere to the study protocol.

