A persistent or significant incapacity or substantial disruption of the ability to conduct normal life functions.

A congenital anomaly/birth defect.

Important medical events that may not result in death, be life-threatening, or require hospitalization may be considered a serious adverse drug experience when, based upon appropriate medical judgment, they may jeopardize the patient or subject and may require medical or surgical intervention to prevent one of the outcomes listed in this definition. Examples of such medical events include allergic bronchospasm requiring intensive treatment in an emergency room or at home, blood dyscrasias or convulsions that do not result in inpatient hospitalization, or the development of drug dependency or drug abuse (21 CFR 312.32).

Important medical events as defined above, may also be considered serious adverse events. Any important medical event can and should be reported as an SAE if deemed appropriate by the Principal Investigator or the INDIND Sponsor, IND Office.

All events occurring during the conduct of a protocol and meeting the definition of a SAE must be reported to the IRB in accordance with the timeframes and procedures outlined in “The University of Texas M. D. Anderson Cancer Center Institutional Review Board Policy for Investigators on Reporting Unanticipated Adverse Events for Drugs and Devices”. Unless stated otherwise in the protocol, all SAEs, expected or unexpected, must be reported to the IND Office, regardless of attribution (within 5 working days of knowledge of the event).

Unless otherwise noted, the electronic SAE application (eSAE) will be utilized for safety reporting to the IND Office and MDACC IRB for participants enrolled at MDACC.

Reporting for all sites:

- **All life-threatening or fatal events**, that are unexpected, and related to the study drug, must have a written report submitted within **24 hours** (next working day) of knowledge of the event to the Safety Project Manager in the IND Office. -
- **Serious adverse events will be captured from the time of the first protocol-specific intervention, until 30 days after the last dose of drug, unless the participant withdraws consent. Serious adverse events must be followed until clinical recovery is complete and laboratory tests have returned to baseline, progression of the event has stabilized, or there has been acceptable resolution of the event.**

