It results in a congenital anomaly/birth defect in a neonate/infant born to a mother exposed to the IMP. It is considered a significant medical event by the investigator based on medical judgment (e.g., may jeopardize the patient or may require medical/surgical intervention to prevent one of the outcomes listed above).

METHODS AND TIMING FOR ASSESSING AND RECORDING SAFETY VARIABLES

The investigator is responsible for ensuring that all AEs and SAEs, that are observed or reported during the study, are collected and reported to the U.S. Food and Drug Administration (FDA), appropriate IRB(s), and Genentech, Inc. in accordance with CFR 312.32 (IND Safety Reports).

Adverse Event Reporting Period

The study period during which all AEs and SAEs must be reported begins after informed consent is obtained and initiation of study treatment and ends 30 days following the last administration of study treatment or study discontinuation/termination, whichever is earlier. After this period, investigators should only report SAEs that are attributed to prior study treatment.

Assessment of Adverse Events

All AEs and SAEs whether volunteered by the patient, discovered by study personnel during questioning, or detected through physical examination, laboratory test, or other means will be reported appropriately. Each reported AE or SAE will be described by its duration (i.e., start and end dates), regulatory seriousness criteria if applicable, suspected relationship to the obinutuzumab (see following guidance), and actions taken.

To ensure consistency of AE and SAE causality assessments, investigators should apply the following general guideline:

Yes

There is a plausible temporal relationship between the onset of the AE and administration of the obinutuzumab and the AE cannot be readily explained by the patient's clinical state, intercurrent illness, or concomitant therapies; and/or the AE follows a known pattern of response to the obinutuzumab and/or the AE abates or resolves upon discontinuation of the obinutuzumab or dose reduction and, if applicable, reappears upon re-challenge.

No

Evidence exists that the AE has an etiology other than the obinutuzumab (e.g., preexisting medical condition, underlying disease, intercurrent illness, or concomitant medication); and/or the AE has no plausible temporal relationship to obinutuzumab administration (e.g., cancer diagnosed 2 days after first dose of obinutuzumab).

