Expected AEs are those AEs that are listed or characterized in the Package Insert or current Investigator Brochure.

Unexpected AEs are those not listed in the Package Insert (P.I.) or current Investigator's Brochure or not identified. This includes AEs for which the specificity or severity is not consistent with the description in the P.I. or Investigator's Brochure. For example, under this definition, hepatic necrosis would be unexpected if the P.I. or Investigator's Brochure only referred to elevated hepatic enzymes or hepatitis.

PROCEDURES FOR ELICITING, RECORDING, AND REPORTING ADVERSE EVENTS

Eliciting Adverse Events

A consistent methodology for eliciting AEs at all patient evaluation timepoints should be adopted. Examples of non-directive questions include:

“How have you felt since your last clinical visit?”

“Have you had any new or changed health problems since you were last here?

Specific Instructions for Recording Adverse Events

Investigators should use correct medical terminology/concepts when reporting AEs or SAEs. Avoid colloquialisms and abbreviations.

Diagnosis versus Signs and Symptoms

If known at the time of reporting, a diagnosis should be reported rather than individual signs and symptoms (e.g., record only liver failure or hepatitis rather than jaundice, asterixis, and elevated transaminases). However, if a constellation of signs and/or symptoms cannot be medically characterized as a single diagnosis or syndrome at the time of reporting, it is acceptable to report the information that is currently available. If a diagnosis is subsequently established, it should be reported as follow-up information.

Deaths

All deaths that occur during the protocol-specified AE reporting period regardless of attribution, will be reported to the appropriate parties. When recording a death, the event or condition that caused or contributed to the fatal outcome should be reported as the single medical concept. If the cause of death is unknown and cannot be ascertained at the time of reporting, report “Unexplained Death”.

Preexisting Medical Conditions

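### The adverse event reporting period can close at study discontinuation, which conflicts with the 30-day SAE window and may leave later non-serious grade 3+ events unrecorded

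*Combined protocol and SAP*

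**What the plan says.** Section 10 of the combined protocol and SAP gives two rules for how long safety events are collected.

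- **Adverse Event Reporting Period** covers all AEs and SAEs. On the closing date, the text is that the period "ends 30 days following the last administration of study treatment or study discontinuation/termination, whichever is earlier". On the opening date, it is that the period "begins after informed consent is obtained and initiation of study treatment". Once the period has closed, the duty narrows: "After this period, investigators should only report SAEs that are attributed to prior study treatment".
- **Reporting for all sites** covers SAEs only. "Serious adverse events will be captured from the time of the first protocol-specific intervention", and capture runs "until 30 days after the last dose of drug, unless the participant withdraws consent". SAEs that are already open are followed further: "Serious adverse events must be followed until clinical recovery is complete and laboratory tests have returned to baseline", or until they stabilise or resolve acceptably.

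Three other places bear on the point.

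- Section 7 lists criteria for study discontinuation. They include disease progression and "Determination by the investigator that it is no longer safe for the patient to continue therapy".
- The Deaths paragraph of Section 10 is tied to the reporting period: "All deaths that occur during the protocol-specified AE reporting period regardless of attribution, will be reported to the appropriate parties".
- Under Method of Analysis, the grade 3+ toxicity rule counts patients with non-haematological toxicity of grade 3 or above. The Table 8 boundaries are 8 of 10, 14 of 20 and 20 of 30. The rule states neither an observation window nor an attribution requirement.

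**The concern.** One rule lets SAE capture end early only if consent is withdrawn. The other adds a second early exit, study discontinuation or termination. A site cannot follow both when a patient leaves the study within 30 days of the last dose.

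For non-serious AEs there is no second rule to fall back on. If the period closes when a patient is taken off for toxicity or progression, the shortened observation falls on patients who may well have further events. Safety is a secondary endpoint and one of the two quantities monitored at interim looks. Any loss would work in one direction, towards too low a recorded toxicity rate.

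**Working it through.** The documents state no figure that this point could reproduce. The check is a comparison of texts, plus arithmetic on dates.

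**1. When the period ends.** Let the last dose be day 0 and study discontinuation be day *d* ≥ 0. The sentence can be read in three ways.

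- *Patient-level discontinuation is itself an end point.* End = min(30, *d*). Days lost against the 30-day SAE rule = 30 − min(30, *d*).

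| *d* | Period ends | Days lost |
|---|---|---|
| 0 | day 0 | 30 − 0 = 30 |
| 7 | day 7 | 30 − 7 = 23 |
| 14 | day 14 | 30 − 14 = 16 |
| 30 or later | day 30 | 30 − 30 = 0 |

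- *The 30 days are counted from both events.* End = min(0, *d*) + 30 = day 30. Nothing is lost. However, a last dose cannot come after study discontinuation, so the earlier date is always 30 days after the last dose and the second limb has no effect.
- *The words mean closure of the whole trial.* The period is cut only for patients whose last dose falls less than 30 days before closure. The end date still conflicts with the SAE rule, but patients who stop for toxicity or progression are not singled out.

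**2. Does coming off treatment count as study discontinuation?** The documents do not define the term. The heading of Section 7 suggests that it does. So do the parallel pregnancy-test schedules: Section 8 asks for a test when lenalidomide is stopped, and the matching line in Appendix 4 says study discontinuation. Against this, the Section 7 safety criterion speaks of continuing therapy, and Appendix 4 also refers separately to discontinuation of study drug. Overall survival and time to next treatment are endpoints, so patients off treatment may remain on study.

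**3. What is still collected after an early close.**

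| Event within 30 days of last dose | Still required? | Where in Section 10 |
|---|---|---|
| SAE, related or not | Yes | Reporting for all sites; SAEs go to the IND Office whatever the attribution |
| Death | Yes | Death is an SAE criterion; the opening safety paragraph includes all deaths |
| SAE already open | Yes, to resolution | Reporting for all sites |
| Non-serious AE, any grade, related or not | No | Only the Adverse Event Reporting Period applies |

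Treatment-related SAEs remain reportable even beyond 30 days.

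**4. When the grade 3+ count changes.** The rule counts patients, so a lost event matters only if all of these hold:

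- it is non-haematological, grade 3 or above, and non-serious;
- it is that patient's first such event;
- it falls after study discontinuation and within 30 days of the last dose;
- it would have been known at an interim look. For the final toxicity rate this last condition drops out.

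A patient removed because of a grade 3+ non-haematological event is already counted. The patients at issue are those removed for progression, for haematological toxicity or for a lower-grade event. The documents do not say how many of them would have such a first event.

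**5. Start of the period.** One rule starts at initiation of treatment, the other at the first protocol-specific intervention, which is not identified. The list of AEs under the Genentech-requested reporting does include, where applicable, events before treatment that are linked to a protocol-mandated intervention. The mismatch is therefore an inconsistency to tidy, not a clear gap.

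**The case against.** The strongest reply is that the sentence need not shorten anything. It may count 30 days from both events, or it may refer to closure of the trial, since Section 7 also speaks of discontinuing and terminating the study as a whole. The first reading leaves the clause with no work to do. The second still leaves the end dates in conflict. Neither removes the need to reconcile the two rules, but together they mean that a zero-day window for patients stopping for toxicity is a possibility and not a certainty.

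It can also be said that the two rules serve different recipients: one is the IND Office rule, and the other sits within the Genentech-requested reporting. That is fair for SAEs, because the shorter period does not cancel the IND Office duty. It does not help with non-serious AEs, for which the IND Office rule sets no window. Nor is the shorter period purely a company matter, since its parent section also names the FDA and the IRBs.

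A reader might infer that unrelated SAEs and deaths go unrecorded. The documents do not support this: the IND Office rule and the inclusion of all deaths in the safety assessment both stand, whatever the Deaths paragraph says. The grade 5 stopping rule is therefore not shown to be affected.

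A reader might also infer that no contact is planned at 30 days after the last dose. Section 8 shows none apart from pregnancy tests, but the Study Calendar (Appendix 2) is not in the text available for review, so this cannot be judged.

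**Conclusion.** The conflict is real but narrow. The two rules disagree on the end of the SAE window and on where collection starts. For non-serious AEs the problem is a window that may be too short; there is no contradiction there, because only one rule covers them.

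Up to 30 days of non-serious AE reporting per discontinued patient could be lost, if study discontinuation includes being taken off treatment and sites stop recording when the duty lapses. The direction is towards a lower recorded toxicity rate and a lower grade 3+ count.

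It is tempting to turn this into a reduced probability of stopping for toxicity. That would need the fraction of patients whose only qualifying event falls in the dropped interval. The documents do not give it and offer nothing to bound it, so no such figure is offered here. The correction is worth making because it is nearly free, not because a large bias has been shown.

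**What to change.** In Section 10, Adverse Event Reporting Period, delete the alternative end date of study discontinuation or termination together with the earlier-of rule. All AEs and SAEs would then be collected until 30 days after the last dose of whichever study drug stops later, unless consent is withdrawn. The Deaths paragraph follows without further change, because it refers to the same period.

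Align the start with Reporting for all sites, that is, the first protocol-specific intervention, and state which procedure that is. If the term study discontinuation is kept anywhere, define it and say whether it differs from stopping study drug.

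The cost is two wording changes, slightly more AE recording after treatment ends, and possibly a slightly higher recorded toxicity rate. No hypothesis, sample size or stopping boundary changes.

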Appendix 1 ECOG Performance Status

[figure not shown]
[figure not shown]
		ECOG PERFORMANCE STATUS*	
Grade	ECOG		
0	Fully active, able to carry on pre-disease performance without restriction		
1	Restricted in physically strenuous activity but ambulatory and able to carry out work of a light or sedentary nature, e.g., light house work, office work		
2	Ambulatory and capable of all selfcare but unable to carry out any work activities. Up and about more than 50% of waking hours		
3	Capable of only limited selfcare, confined to bed or chair more than 50% of waking hours		
	Completely disabled. Cannot carry on any selfcare. Totally confined to bed or chair		
	Dead		

*As published in Am. J. Clin.

Oneal:

Oken, M.M., Creech, R.H., Tanney, D.C., Horton, J., Davis, T.E., McFadden, E.T., Carbone, P.P.: *Toxicity*

And Response Criteria Of The Eastern Cooperative Oncology Group. Am J Clin Oncol 5:649-655, 1982.

Appendix 3Current NCI Common Terminology Criteria for Adverse Events (CTCAE)

In the present study, toxicities will be graded according NCI CTCAE, version 4.0.

Please use the following link to the NCI CTCAE website:

http://ctep.cancer.gov/protocolDevelopment/electronic_applications/etc.htm

Appendix 4 Risks of Fetal Exposure, Pregnancy Testing Guidelines and Acceptable Birth Control Methods.

Lenalidomide is structurally related to thalidomide. Thalidomide is a known human teratogenic active substance that causes severe life-threatening birth defects. An embryofetal development study in animals indicates that lenalidomide produced malformations in the offspring of female monkeys who received the drug during pregnancy. The teratogenic effect of lenalidomide in humans cannot be ruled out. Therefore, a risk minimization plan to prevent pregnancy must be observed.

All study participants must be registered into the mandatory Revlimid REMS® program, and be willing and able to comply with the requirements of Revlimid REMS®.

Criteria for females of childbearing potential (FCBP)

This protocol defines a female of childbearing potential as a sexually mature woman who: 1) has not undergone a hysterectomy or bilateral oophorectomy or 2) has not been naturally postmenopausal (amenorrhea following cancer therapy does not rule out childbearing potential) for at least 24 consecutive months (i.e., has had menses at any time in the preceding 24 consecutive months).

Counseling

For a female of childbearing potential, lenalidomide is contraindicated unless all of the following are met (i.e., all females of childbearing potential must be counseled concerning the following risks and requirements prior to the start of lenalidomide study therapy):

- She understands the potential teratogenic risk to the unborn child
- She understands the need for effective contraception, without interruption, 4 weeks before starting study treatment, throughout the entire duration of study treatment, dose interruption and 28 days after the end of study treatment

She should be capable of complying with effective contraceptive measures

- She is informed and understands the potential consequences of pregnancy and the need to notify her study doctor immediately if there is a risk of pregnancy
- She understands the need to commence the study treatment as soon as study drug is dispensed following a negative pregnancy test
- She understands the need and accepts to undergo pregnancy testing based on the frequency outlined in this protocol

- She acknowledges that she understands the hazards and necessary precautions associated with the use of lenalidomide

The investigator must ensure that for females of childbearing potential:

- Complies with the condition for pregnancy risk minimization including confirmation that she has an adequate level of understanding
- Acknowledge the aforementioned requirements
- For a female NOT of childbearing potential, lenalidomide is contraindicated unless all of the following are met (i.e., all females NOT of childbearing potential must be counseled concerning the following risks and requirements prior to the start of lenalidomide study therapy):
- She acknowledges that she understands the hazards and necessary precautions associated with the use of lenalidomide

Traces of lenalidomide have been found in semen. Male patients taking lenalidomide must meet the following conditions (i.e., all males must be counseled concerning the following risks and requirements prior to the start of lenalidomide study therapy):

Understand the potential teratogenic risk if engaged in sexual activity with a pregnant female or a female of childbearing potential

- Understand the need for the use of a condom even if he has had a vasectomy, if engaged in sexual activity with a pregnant female or a female of childbearing potential.

Contraception

Females of childbearing potential (FCBP) enrolled in this protocol must agree to use two reliable forms of contraception simultaneously or to practice complete abstinence from heterosexual contact during the following time periods related to this study: 1) for at least 28 days before starting study drug; 2) while participating in the study; 3) dose interruptions; and 4) for at least 28 days after study treatment discontinuation.

The two methods of reliable contraception must include one highly effective method and one additional effective (barrier) method. FCBP must be referred to a qualified provider of contraceptive methods if needed. The following are examples of highly effective and additional effective methods of contraception:

- **Highly effective methods:**

Intrauterine device (IUD)

Hormonal (birth control pills, injections, implants) Tubal ligation Partner's vasectomy

- **Additional effective methods:**

Male condom
Diaphragm Cervical Cap

Implants and levonorgestrel-releasing intrauterine systems are associated with an increased risk of infection at the time of insertion and irregular vaginal bleeding. Prophylactic antibiotics should be considered particularly in patients with neutropenia.

Pregnancy testing

Medically supervised pregnancy tests with a minimum sensitivity of 50 mIU/mL must be performed for females of childbearing potential, including females of childbearing potential who commit to complete abstinence, as outlined below.

Before starting study drug

Female Patients:

FCBP must have two negative pregnancy tests (sensitivity of at least 50 mIU/mL) prior to starting study drug. The first pregnancy test must be performed within 10 to 14 days prior to the start of study drug and the second pregnancy test must be performed within 24 hours prior to the start of study drug. The patient may not receive study drug until the study doctor has verified that the results of these pregnancy tests are negative.

Male Patients:

Must practice complete abstinence or agree to use a condom during sexual contact with a pregnant female or a female of childbearing potential while participating in the study, during dose interruptions and for at least 28 days following study drug discontinuation, even if he has undergone a successful vasectomy.

During study participation and for 28 days following study drug discontinuation **Female Patients:**

FCBP with regular or no menstrual cycles must agree to have pregnancy tests weekly for the first 28 days of study participation and then every 28 days while on study, at study discontinuation, and at day 28 following study drug discontinuation. If menstrual cycles are irregular, the pregnancy testing must occur weekly for the first 28

days and then every 14 days while on study, at discontinuation.
study14and 28 following study drug discontinuation, and at days

At each visit, the Investigator must confirm with the FCBP that she is continuing to use two reliable methods of birth control.

- Counseling about pregnancy precautions and the potential risks of fetal exposure must be conducted at a minimum of every 28 days.
- If pregnancy or a positive pregnancy test does occur in a study patient, study drug must be immediately discontinued.
- Pregnancy testing and counseling must be performed if a patient misses her period or if her pregnancy test or her menstrual bleeding is abnormal. Study drug treatment must be discontinued during this evaluation.

Females must agree to abstain from breast feeding during study participation and for at least 28 days after study drug discontinuation.

Male Patients:

- Counseling about the requirement for complete abstinence or condom use during sexual contact with a pregnant female or a female of childbearing potential and the potential risks of fetal exposure to lenalidomide must be conducted at a minimum of every 28 days.

If pregnancy or a positive pregnancy test does occur in the partner of a male study patient during study participation, the investigator must be notified immediately.

Additional precautions

Patients should be instructed never to give this medicinal product to another person and to return any unused capsules to the study doctor at the end of treatment.

- Female patients should not donate blood during therapy and for at least 28 days following discontinuation of study drug.
- Male patients should not donate blood, semen or sperm during therapy or for at least 28 days following discontinuation of study drug.
- Only enough study drug for one cycle of therapy may be dispensed with each cycle of therapy.

Pregnancies:

Pregnancies and suspected pregnancies (including a positive pregnancy test regardless of age or disease state) of a female subject occurring while the subject is on IP (Investigational Product), or within (insert time-frame which must be at least 28 days of the subject's last dose of IP), are considered immediately reportable events. IP is to be discontinued immediately. The pregnancy, suspected pregnancy, or positive pregnancy

test must be reported to Celgene Drug Safety immediately by facsimile, or other appropriate method, using the Pregnancy Initial Report Form, or approved equivalent form. The female subject should be referred to an obstetrician-gynecologist, preferably one experienced in reproductive toxicity for further evaluation and counseling.

The Investigator will follow the female subject until completion of the pregnancy, and must notify Celgene Drug Safety immediately about the outcome of the pregnancy (either normal or abnormal outcome) using the Pregnancy Follow-up Report Form, or approved equivalent form. If the outcome of the pregnancy was abnormal (e.g., spontaneous or therapeutic abortion), the Investigator should report the abnormal outcome as an AE. If the abnormal outcome meets any of the serious criteria, it must be reported as an SAE to Celgene Drug Safety immediately by facsimile, or other appropriate method, within 24 hours of the Investigator's knowledge of the event using the SAE Report Form, or approved equivalent form.

All neonatal deaths that occur within 28 days of birth should be reported, without regard to causality, as SAEs. In addition, any infant death after 28 days that the Investigator suspects is related to the in utero exposure to the IP should also be reported to Celgene Drug Safety immediately by facsimile, or other appropriate method, within 24 hours of the Investigator's knowledge of the event using the SAE Report Form, or approved equivalent form.

Male Subjects

If a female partner of a male subject taking investigational product becomes pregnant, the male subject taking IP should notify the Investigator, and the pregnant female partner should be advised to call their healthcare provider immediately.

